3.1.1 Experimental Design

This is a single-arm assessment of AHI responder rate for treatment of obstructive sleep apnea compared to a performance goal (PG). Patients with 6-month post-treatment AHI measurements will be counted as a responder if they meet the performance goal. A subject will be counted as a non-responder (regardless of AHI measurement at 6 months) under the following circumstances:

- a. Death (any cause) between treatment and the 6-month follow-up
- b. Unsuccessful radiofrequency treatment attempt
- c. Need for an alternative OSA treatment before the 6-month follow-up
- d. Subjects who abandon the study
- e. Subjects who exit the study after the last treatment, but before the 6-month follow-up

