calls. In addition, three patients were excluded because of additional treatment after completion of RFA (2 CPAP, 1 surgery).

Discussing the limitations of their study, Friedman et al. (2007)⁵⁹ attribute one of the study' limitations to the large number of patients who are lost to follow-up, and declare "Unfortunately, many patients are not willing to return for a follow-up PSG". Based on an "intent-to-treat" analysis the cure rate was 37.2%. The authors estimate, however, that the "true" success rate is closer to 47.5% and state that, "it is possible that most of the patients who have had elimination of symptoms are those who are least likely to participate in the follow-up PSG". In order to increase participation in the long-term follow-up visit, patients were offered free adjunctive treatment such as additional Pillar implants and radiofrequency tongue base reduction based on need as determined by the postoperative PSG. Apparently, most patients who were willing to participate in the follow-up visit, were those who had persistent snoring or symptoms and wanted additional treatment⁵⁹.

The problem of a high number of dropouts in long-term follow-ups is not limited to RFA studies. Walker et al. (2007)⁷⁰, for example, conducted a study with an extended follow-up (15 months) that was based on an initial study with 90-days follow-up. Out of 53 patients that were enrolled to the initial study, 13 patients were either unable to be contacted or declined further participation; one site with seven patients from the initial study did not participate in the extended follow-up; seven patients did not meet the study inclusion criteria and four patients had other treatments for OSA (e.g., nasal CPAP, uvulopalatopharyngoplasty, laser-assisted uvulopalatoplasty) rendered during the extended follow-up period. Thus, the extended follow-up included only 22 patients (41.5%).

Doff et al (2013)⁷¹, conducted a randomized study that compared outcomes of oral appliances(Group I) and CPAP (Group II) after 2 years follow-up. Out of 51 patients in Group I and 52 patients in Group II that started the clinical trial, only 29 and 37 patients (respectively) finished the 2-years follow-up study (64%).

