5.7 Visit 7- Final Follow-up Visit (6-Months later after last RF treatment)

The patient will undergo complete post-treatment evaluations including sleep history and physical examination (including height, weight, and blood pressure) as done in Baseline Visit. The patient will be asked to complete questionnaires including Epworth Sleepiness Scale (ESS), Functional Outcomes of Sleep Questionnaire (FOSQ) and 10 cm VAS concerning pain, snoring (bed partner), speech, and

swallowing. In addition, each patient will undergo a second PSG sleep study not later than 30 days after the Final Study Visit. The PSG sleep study will be conducted using standard techniques in the sleep laboratory as defined in section 5.2 above.

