5.8 Visit 8 – Final Study Visit (after the PSG sleep study)

Shortly after the 2nd PSG study, the study physician will inform the patient on his/her study results and medical condition and will give recommendations for ongoing management as needed.

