6 DURATION

This study has a minimum of eight visits. The first visit, the Screening Visit, is planned for determining whether patient qualifies for the study. This visit will take up to 1 hour. In the second visit, the Baseline Visit, which occurs up to 2 weeks later, standard medical history, demographics and various questionnaires will be obtained from the patient. In addition, the patient will undergo a Müller's Maneuver and will be sent to the sleep lab for a PSG study (one night). This visit will last about 60 minutes.

The third visit is the first RF treatment session and will last about 1 hour. The fourth and fifth visits involve additional RF treatments and will last about one hour each. The first follow-up visit will occur 6 weeks after the third treatment visit and will last as well about 1 hour. The 7th visit, the 6-month follow-up visit, will occur 6 months later and will be no more than 1 hour. At the end of this visit the patient will be admitted to a sleep labor for undergoing the 2nd PSG study. Finally, the 8th and final Visit will last about 30 minutes. The patients may require additional visits in case of complications that are needed to be treated in the hospital or if they have a question or concern. The entire duration of the study for an individual patient is no longer than 24 weeks plus 6 months of follow-up.

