APPENDIX I

TIME TABLE (STUDY FLOW CHART)

	Visit 1 Screening	Visit 2 Baseline Intake	Visit 3 1 st RFA	Visit 4 2 nd RFA	Visit 5 3 rd RFA	Visit 6 Follow-up (6 weeks post- treatment)	Visit 7 Final Follow-up (6 months post- treatment)	Visit 8 Final Study Visit
Time	Week 0	Week 2	(up to) Week 6	(up to) Week 12	(up to) Week 18	(up to) Week 24	6 months later	shortly after last PSG
Intake and consent form	X							
Inclusion criteria	X							
Medical history	X							
Physical examination	X		X (on the day of the RF treatment, 3 and 10 days later)	X (on the day of the RF treatment, 3 and 10 days later)	X (on the day of the RF treatment, 3 and 10 days later)	X	X	X
VAS snoring		X	X	X	X	X	X	
WatchPat (patients screening before PSG)	X							

PSG sleep study (AHI)		X No longer than 90 days after enroll- ment					X Within 4 weeks	
oxygen desaturation index (ODI)		X					X	
Müller's Manoeuvre		X						
Epworth Sleepiness Scale (ESS)		X		X	X	X	X	
Functional Outcomes of Sleep Questionnaire (FOSQ)		X		X	X	X	X	
VAS pain, speech, and swallowing			X (1, 3 and 7 days after RF treatment)	X (1, 3 and 7 days after RF treatment)	X (1, 3 and 7 days after RF treatment)	X	X	
Adverse Event Form		X	X	X	X	X	X	X
RFA Treatment			X	X	X			
End of Study Form								X
Study results and medical consultation								X

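### The end of the non-responder window is undefined against an inconsistently timed 6-month PSG, and a treated patient who attends Visit 7 but has no PSG can be dropped instead of scored as a failure

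*Combined protocol and SAP*

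**What the plan says.** Section 3.1.1 lists five circumstances that make a subject a non-responder whatever the AHI. Three have an end point: death (rule a), alternative therapy (rule c, "Need for an alternative OSA treatment before the 6-month follow-up") and exit (rule e, "Subjects who exit the study after the last treatment, but before the 6-month follow-up"). Rules b (unsuccessful treatment attempt) and d (abandoning the study) have none. Section 3.3.1 repeats the list for the secondary endpoints.

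Response is decided on the 6-month PSG (section 3.1). The protocol times it as follows:

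- Section 3.1: at the final follow-up examination.
- Section 6: "The 7th visit, the 6-month follow-up visit, will occur 6 months later", and then "At the end of this visit the patient will be admitted to a sleep labor for undergoing the 2nd PSG study".
- Section 5.7: "each patient will undergo a second PSG sleep study not later than 30 days after the Final Study Visit". By title, the visit of that name is Visit 8, which comes after the PSG: "5.8 Visit 8 – Final Study Visit (after the PSG sleep study)".
- Appendix I, Visit 7 column: "Within 4 weeks".

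On missing data, section 8.5 treats subjects lost to follow-up as failures. Section 3.1.2 limits the primary analysis to subjects who had all three treatments and the 6-month assessment. Section 8.4 limits the Full Analysis Set to treated subjects who completed all eight visits.

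**The concern.** Two kinds of patient fall between these provisions.

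The first attends Visit 7, starts another OSA therapy, and then has the PSG. If the 6-month follow-up is Visit 7, rule c has already closed, and any benefit of the new therapy is counted as response to RFA. No section bars such therapy before the PSG or says how the patient is scored.

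The second attends Visit 7, stays in contact, and never has a scorable PSG. This patient did not exit before the visit and is not lost to follow-up in the ordinary sense. The plan does not clearly count the patient as a failure, and two of its population definitions allow the patient to be left out.

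This is a single-arm trial with one proportion tested against 50%. Removing a patient from the denominator instead of scoring that patient as a failure always gives a higher observed rate. Section 2.5 raises the risk itself, citing a study that found "many patients are not willing to return for a follow-up PSG".

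**Working it through.** **1. The plan's own figure.** Inputs from section 3.2: n = 43, P0 = 0.50, P1 = 0.70, reject if Z ≥ 1.96. The cut-off is the smallest count at or above 43/2 + 1.96·√(43/4) = 27.93, so 28. Exact binomial: P(X ≥ 28 | 43, 0.5) = 0.0330 and P(X ≥ 28 | 43, 0.7) = 0.8081. Both match section 3.2, and 0.8081 matches the 80.8% in section 8.3. The boundary therefore lies between 27 (Z = 1.68, exact p = 0.063) and 28 (Z = 1.98, exact p = 0.033), so one patient can decide the result.

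**2. Other therapy between Visit 7 and the PSG.** Section 2.5 gives two extended follow-ups.

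- In one, 3 patients had additional treatment. The denominator is between 29 (participants) and 46 (eligible), over about 23 months (Table 1).
- In the other, 4 of 53 had other treatment between 90 days and 15 months, so over about 12 months.

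Scaled to 43 patients and one month:

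- 43 × 3 / 46 / 23 = 0.12
- 43 × 3 / 29 / 23 = 0.19
- 43 × 4 / 53 / 12 = 0.27

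This assumes a constant rate and the longest gap that the protocol allows.

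**3. How the patient with no PSG is classified.**

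| Provision | Applies to a patient who attends Visit 7, stays in contact and has no PSG? |
|---|---|
| 3.1.1 rules a, b, c | No |
| 3.1.1 rule d | Arguable; abandoning the study is not defined |
| 3.1.1 rule e | No, if the 6-month follow-up is Visit 7 |
| 8.5 loss to follow-up | Not clearly |
| 13.4 adjudication | Withdrawals only |
| 3.1.2 primary analysis | Can exclude, if the assessment includes the PSG |
| 8.4 Full Analysis Set | Can exclude, because Visit 8 follows the PSG |

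**4. Effect on the test.** The documents give no count, so 1 to 3 such patients are assumed, all of them non-responders, with a true rate of 50% among all 43 treated. With k dropped, n = 43 − k, the rate among those analysed is 21.5/n, and the cut-off is the smallest count at or above n/2 + 1.96·√(n/4).

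| k dropped | n | Cut-off | Rate analysed | One-sided error |
|---|---|---|---|---|
| 0 | 43 | 28 | 0.500 | 0.033 |
| 1 | 42 | 28 | 0.512 | 0.031 |
| 2 | 41 | 27 | 0.524 | 0.058 |
| 3 | 40 | 27 | 0.5375 | 0.055 |

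The error does not rise steadily because the cut-off moves in whole patients.

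For one data set: 27 responders with three patients dropped is 27/40, Z = 2.21, exact p = 0.019. The same 27 with those three scored as failures is 27/43, Z = 1.68, exact p = 0.063. The verdict reverses.

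**The case against.** **The window may already include the PSG.** A reader might infer that the rules definitely close before the PSG. The documents do not establish this. Section 6, which names Visit 7 as the 6-month follow-up, also puts the PSG at the end of that visit, and section 3.1 places it at the final follow-up examination. Sections 3.1, 7 and 8.1 treat AHI as something obtained at the 6-month follow-up. On that reading rules a, c and e reach the PSG. The 30-day allowance in section 5.7 is counted from a visit that by title follows the PSG, so it makes sense only if Visit 7 was meant. Appendix I still allows up to 4 weeks. What stands is a conflict and an undefined term, not a proven early closure.

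**Therapy in the gap is unlikely.** Enrolled patients have failed or not tolerated CPAP and have declined oral appliances (section 4.1.1). Results and final advice follow the PSG (section 5.8). Rule c speaks of need, so a need recorded before Visit 7 counts even if therapy starts later. This stands, and it agrees with the estimate of 0.1 to 0.3 patients.

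**The bias need not favour the device.** A reader might infer that dropping these patients must overstate the true response rate. Section 2.5 also reports the suggestion that patients whose symptoms resolved are the least likely to return. If so, dropping them could understate the true rate. The all-non-responder assumption is therefore one end of a range. It remains true that dropping gives a higher observed rate than the failure scoring the plan uses elsewhere.

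**One missing patient does not double the error.** An exact 0.025 cut-off gives 0.016 with none missing and 0.031 with one, which invites that inference. The jump comes from the cut-off going from 29 of 43 to 28 of 42. Under the Z rule in section 3.2 the error goes from 0.033 to 0.031.

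**Rule d might cover the patient with no PSG.** It might, but the term is undefined, and sections 3.1.2 and 8.4 could still exclude the patient.

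**Conclusion.** The concern holds as a gap in definition. The protocol gives incompatible times for the PSG that decides response, and ends three non-responder rules at a point it does not define. The effect through other therapy is small: 0.1 to 0.3 expected patients, on the reading that leaves the longest gap.

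The patient with no PSG matters more. Failure scoring in sections 3.1.1 and 8.5 and exclusion in sections 3.1.2 and 8.4 give different answers, and two or three such patients could change the trial's result. The error rates of 0.058 and 0.055 rest on an assumed count, on all of these patients being non-responders, and on a true rate of 50%; none of these comes from the documents. No stated sample size, alpha or power figure is wrong.

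**What to change.** - In sections 3.1.1 and 3.3.1, end rules a, c and e at the date of the 6-month PSG.
- State in section 3.1.1 that a treated subject with no scorable 6-month PSG is a non-responder, whether or not Visit 7 was attended.
- Amend sections 3.1.2 and 8.4 so that they do not exclude that subject. A change to 3.1.1 alone could be overridden by them.
- Reconcile the PSG timing in sections 3.1, 5.7 and 6 and Appendix I, including the visit from which section 5.7 counts.
- Confirm that any other OSA therapy and its start date are recorded up to the PSG. The documents do not show this explicitly.

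The cost is wording, plus a case report form item if that therapy is not already captured. Planned n (43, or 48 with dropouts), exact alpha (0.033) and power (0.808) do not change. The downside is that the reported responder rate may be slightly lower, and would be conservative if some patients without a PSG had in fact responded. The analysis without lost-to-follow-up subjects in section 8.5 could be extended to these patients to show the difference.

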3.1.2 Subjects included in the Primary Efficacy Objective Analysis

The primary efficacy analysis will include all subjects who received all three radiofrequency treatment procedures and the follow-up assessment at 6-months post-treatment.

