2.2 Scale

The study will be conducted at a maximum of 3 centers in which at least one study center will be in the United States. Patients will be enrolled to provide data from up to 48 subjects. Data from 43 subjects is required to demonstrate efficacy and we count 10% for dropouts (Section 3.2 Sample Size Rational). When the treatment limit of 48 subjects is reached, Sponsor may opt to submit for expanded access.

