3.2 Sample Size Rationale

The sample size proposed for this study is 48 patients. This sample size is comparable to that used in performance and safety studies using radiofrequency ablation for the treatment of upper airways (soft palate and base of tongue, Table 1). In fact, considerable clinical data on the efficacy and safety RFA in OSAS is available from prior studies on this topic.

Recommended sample size is n=48. Sample size is calculated for o the proportion of participants who meet the successes criteria as defined by the performance goal (PG) (Section 3.1).

The following sample size considerations are based on the assumptions that PG=50% with 5% significance level and 80% power.

The sample size of n=43 +10% dropouts, i.e. n=48, is calculated by using the normal approximation for the z-score for testing inference about a single proportion p;

$$H_0: P_0 < 50\%$$

$$H_1: P_1 \geq 50\%$$

$$\text{and } P_1 - P_0 \geq 20\%$$

Below is the output of PASS12 NCSS program for sample size calculation:

Analysis of One Proportion Tests								
Numeric Results for testing $H_0: P = P_0$ versus $H_1: P > P_0$								
Test Statistic: Z Test using S (P0)								
Power	Proportion	Given H0 (P0)	Given H1 (P1)	Difference (P1 - P0)	Target Alpha	Actual Alpha	Beta	Reject H0 If Z \geq This
$\alpha=0.025$								
0.8029	187	0.5000	0.6000	0.1000	0.0250	0.0285	0.1971	1.9600
0.8112	82	0.5000	0.6500	0.1500	0.0250	0.0299	0.1888	1.9600
0.8081	43	0.5000	0.7000	0.2000	0.0250	0.0330	0.1919	1.9600
0.81	26	0.5000	0.7500	0.2500	0.0250	0.0378	0.1805	1.9600

Note that the one the actual exact Alpha of 0.033 will meet the two sided 5% significance.

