8.3 Statistical Power Considerations

According to the sample size calculation (section 3.2) the actual expected power is 80.8%.

Seite 36 von 54

Protocol 990211 RAMOSA

RFA for multi-level OSA

Protocol version 6.0 from 26th September 2014

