8.5 Handling of Missing Data, Subject Withdrawals, and Treatment Failures

Subjects that are lost-to-follow-up will be categorized as treatment failures from the time point of dropout forward. Sensitivity analyses will also be conducted excluding lost-to-follow-up subjects to see what impact, if any, they might have on the overall results of clinical activity. Time-to-event analyses will consider these subjects as censored at the lost-to-follow-up time point. All data will be recorded on a CRF forms and will be subjected to regular monitoring.

Every effort will be made to follow subjects for study observation and encourage compliance with study measurements to minimize the amount of missing data.

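### Section 3.1.2 drops from the primary analysis subjects whom 3.1.1 and 8.5 score as failures, nothing says which rule prevails, and the choice can reverse the primary verdict

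*Combined protocol and SAP*

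**What the plan says.** - **Section 3.1.2** sets the primary population: "The primary efficacy analysis will include all subjects who received all three radiofrequency treatment procedures and the follow-up assessment at 6-months post-treatment".
- **Section 3.1.1** lists five circumstances that make a subject a non-responder whatever the 6-month AHI: (a) death, (b) an unsuccessful treatment attempt, (c) need for another OSA treatment, (d) abandoning the study, and (e) "Subjects who exit the study after the last treatment, but before the 6-month follow-up".
- **Section 8.5** adds: "Subjects that are lost-to-follow-up will be categorized as treatment failures from the time point of dropout forward". It then ranks the alternative below this: "Sensitivity analyses will also be conducted excluding lost-to-follow-up subjects".
- **Section 8.4** limits the Full Analysis Set (FAS) to treated subjects who completed all 8 visits. The Safety Analysis Set is everyone treated.
- **Section 8.1** speaks only of all included subjects. **Section 8.2** calls for intention-to-treat and as-treated analyses of all enrolled subjects without naming one as primary. **Section 13.4** brings in withdrawals due to therapy failure.
- **Sizing.** Section 2.2: "Data from 43 subjects is required to demonstrate efficacy and we count 10% for dropouts". Section 3.2: "The sample size of n=43 +10% dropouts, i.e. n=48, is calculated by using the normal approximation". Section 8.3: "the actual expected power is 80.8" per cent.

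**The concern.** The primary endpoint is a single proportion tested against a fixed 50% goal, so the denominator matters as much as the numerator. Someone who dies or exits before 6 months has no 6-month assessment. Section 3.1.2 therefore removes that person, while 3.1.1 and 8.5 keep the same person as a failure. Under 3.1.2, rules (a) and (e) have nothing to act on. Rule (d) has almost nothing; one exception is a subject who attends Visit 7 and leaves before the sleep study, which section 5.7 allows up to 30 days later. The sensitivity analysis in 8.5 then largely repeats the primary one.

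Two analysts following different sections could use 43 and 48 as the denominator for the same data and report opposite conclusions. The choice could be made after the responder count is known.

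**Working it through.** **Inputs.** Goal P0 = 0.50 (3.1.3). Design rate P1 = 0.70 (3.2, 8.1). 43 subjects with data and 48 in total (2.2, 3.2), so 5 planned dropouts. Tests named: one-sided 97.5% confidence interval (3.1); Z using the null variance, reject at Z ≥ 1.96 (3.2); one-sided 95% interval by normal approximation, and exact binomial p (8.1). Section 8.1 gives no alpha for the exact p; one-sided 0.025 is used here.

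**Assumption.** 48 subjects are treated (2.2: "When the treatment limit of 48 subjects is reached") and all dropouts leave after the first treatment and before the 6-month assessment.

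**Step 1: the plan's own figure.** Z = (x/n − 0.5)/√(0.25/n). For n = 43, the smallest x with Z ≥ 1.96 is 28 (Z = 1.98). P(X ≥ 28 | 43, 0.5) = 0.0330 and P(X ≥ 28 | 43, 0.7) = 0.8081. Both match 3.2, so the 80.8% is the power for 43 subjects with data.

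**Step 2: one result, two denominators.** Lower bound = p̂ − z√(p̂(1 − p̂)/n).

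| | 29/43 | 29/48 |
|---|---|---|
| Rate | 67.4% | 60.4% |
| Z | 2.29 | 1.44 |
| Exact one-sided p | 0.016 | 0.097 |
| Lower bound, one-sided 95% | 0.557 | 0.488 |
| Lower bound, one-sided 97.5% | 0.534 | 0.466 |
| Verdict | pass | fail |

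**Step 3: how often the verdicts differ.** Minimum responders needed:

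| Test | n = 43 | n = 48 |
|---|---|---|
| 95% bound | 27 | 30 |
| Z ≥ 1.96, or 97.5% bound | 28 | 31 |
| Exact, 0.025 | 29 | 32 |

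Opposite verdicts arise for 27–29, 28–30 and 29–31 responders respectively. Only 29 lies in all three ranges, and P(X = 29 | 43, 0.7) = 0.12. The next table gives the probability of opposite verdicts at a 70% completer rate. The counts of 3 and 8 dropouts are an assumed range.

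| Dropouts of 48 | 95% bound | 97.5% bound | Z ≥ 1.96 | Exact 0.025 |
|---|---|---|---|---|
| 3 | 16% | 20% | 11% | 24% |
| 5 | 30% | 35% | 35% | 38% |
| 8 | 50% | 61% | 51% | 59% |

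Z and the 97.5% bound share cut-offs at n = 43 and 48. They do not at 45 (30 against 29) or 40 (27 against 26), so they are listed separately.

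**Step 4: power.** If 70% is a completer rate and 10% dropouts count as failures, the all-treated rate is 0.70 × 0.90 = 0.63.

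| | 95% bound | Z or 97.5% bound | Exact 0.025 |
|---|---|---|---|
| 43 with data, rate 0.70 | 88% | 80.8% | 71% |
| 48 treated, rate 0.63 | 59% | 47% | 36% |
| 48 treated, rate 0.70 | 90.0% | 83.6% | 74.9% |

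**The case against.** The best defence is that 3.1.2 simply governs. It carries the heading for the primary population, the FAS in 8.4 is also a completer set, and the sizing treats dropouts as an addition to 43 subjects with data. This is a fair reading, and keeping completers as primary would be a repair grounded in the documents. But it leaves rules (a) and (e) without effect and inverts the order of main and sensitivity analysis in 8.5. The intention-to-treat wording in 8.2 also points the other way.

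Other limits stand:

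- The 43-against-48 contrast needs every dropout to occur after treatment starts. The plan does not say so, and the contrast shrinks if some leave before the first treatment.
- Section 3.1 also defines surgical success as at least 50% of participants meeting the reductions. Read as a point estimate, 29/48 (60.4%) meets it. That is a definition, not an inferential test.
- Sections 3.2 and 8.3 never say whether 70% refers to completers or to all treated subjects.

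A reader might infer that 3.1.2 empties every rule in 3.1.1. It does not: rule (c) still applies to someone who needs another treatment but completes follow-up, and part of rule (b) survives. A reader might also infer that dropping non-completers always raises the response rate. Usually it does, but 3.1.2 also removes partly treated subjects who stay in the study and might respond. In the 29/43 example, though, at least 4 of the 5 excluded would have to be responders to reverse the direction (33/48 = 68.8% against 67.4%).

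**Conclusion.** The contradiction is real and must be fixed before analysis: the primary denominator is not uniquely defined. With 48 treated and 5 dropouts after treatment starts, the chance that the two rules disagree is 30% to 38%, depending on the test, if completers respond at 70%. With 3 to 8 dropouts it ranges from 11% to 61%. The example of 29 shows that the conflict can decide the trial under every named inferential test. It does not show that most results would flip.

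Nor do the documents support saying flatly that the trial is underpowered. Power falls to 59%, 47% or 36% only if 70% is a completer rate and dropouts count as failures. If 70% is the rate among all treated, power is 90.0%, 83.6% or 74.9%. What can be said is that 80.8% describes 43 subjects with data and cannot be carried over to the other rule without restating it.

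**What to change.** 1. **Section 3.1.2:** declare one primary set. The recommended set is all subjects who receive at least one treatment (the Safety Analysis Set population), with the non-responder rules of 3.1.1 and 8.5 applied. The choice belongs to the sponsor, but only one set can be primary.
2. **Sensitivity analyses:** keep the present 3.1.2 completer set as a named one, alongside the analysis in 8.5. They are not the same, because 8.5 excludes only subjects lost to follow-up, while the completer set also drops deaths and partly treated subjects.
3. **Section 3.1.1:** state how a subject with fewer than three treatments and a 6-month sleep study is scored, and whether rule (b) covers that case.
4. **Sections 8.1, 8.2, 8.4 and 13.4:** align them with the chosen set. In 8.4, either remove the all-8-visits condition, which makes the FAS identical to the Safety Analysis Set, or say that the FAS is not used for the primary endpoint.
5. **Sections 3.2 and 8.3:** say whether 70% is a completer or an all-treated rate, and restate the power for the chosen set and test.

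**Cost:** wording changes that mostly apply rules already written, with no added patients. The downside is that the stated power falls below the 80% target if 70% is a completer rate.
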